6.2 Demographics and Subject Characteristics

6.2.1 Completion of enrollment

Summarize all screenings and the number of failed screenings. Summarize the number and proportion of participant in the randomized population who used the investigational product by randomization, who did not use the investigational product by randomization, who did not use the investigational product, who completed the trial, and who did not complete the trial; the number and proportion of participant who did not complete the trial; the number and proportion of participant who did not complete the trial will be summarized in detail with the reasons for withdrawal from the trial on the trial summary page.

List participants in the randomized population who did not complete the trial in detail. List participants who did not enter the PPS (with reasons for scheme violation) in detail.

6.2.2 General Information

- (1) Evaluation Indicators
 - 1) Demographic information: Age, gender, nationality, height and weight;
 - 2) General Condition: medical history, allergic history.
 - 3) Deep vein indwelling catheterization and peripheral skin evaluation status: Insertion site, insertion type, duration of insertion (days), with or without blood oozing after puncture placement, whether other products were applied, whether emergency insertion was performed, whether skin assessment around the insertion site was performed, skin assessment around the insertion site (including erythema, edema, pruritus score and whether skin infection was diagnosed);
 - ♦ Methodology for calculating relevant indicators:
 - ✓ Age (years) = (date of informed consent date of birth + 1) / 365.25, rouding to whole numbers
 - ✓ Duration of tube insertion (days) = date of randomization date of tube insertion + 1
- (2) Evaluation method

FAS was used for evaluation.

The demographic data, general conditions were described accordingly to their numerical characteristics and quantitative indicators were compared between the two groups of participants using t-test/Wilcoxon rank sum test; qualitative indicators were compared between the two groups of participants using chi-square test/Fisher exact probability method.

Summary of the evaluation of deep vein indwelling catheterization and surrounding skin at the level of the insertion site. The two groups of quantitative indicators were compared using t-test/Wilcoxon rank sum test according to their corresponding numerical characteristics description; and the two groups of qualitative indicators were compared using chi-square test/Fisher exact probability method.

In addition, a list of data on medical history, allergic history, deep vein indwelling catheterization prior to enrollment and skin evaluation around the insertion site, and previous/concomitant medication was made for both groups of participants.

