10.2.2 Visit 1/Enrollment Visit/Baseline Visit (Study Day 0)

The following procedures will be completed at Visit 1:

1. Confirmation of subjects' eligibility and assessment of inclusion/exclusion criteria;
2. Randomization of patients who met the inclusion criteria;
3. Assessment of the skin condition around the catheter site.
4. Performing immediate dressing changes at all DVC insertion sites based on subjects' conditions at enrollment, using either the subject device 3M™ Tegaderm™ CHG I.V. Securement Dressing or the 3M™ Tegaderm™ Transparent Film Dressing as per randomization results, and following routine departmental nursing procedures;

The following data will be collected at the first visit:

1. Demographic information (height, weight, gender, age at consent);
2. Past medical history and allergic history, collected according to HIS records: Collection of medical and allergic history within the last 3 months related to the inclusion/exclusion criteria, including but not limited to diabetes, immune-related diseases, skin conditions, etc.;
3. Vital signs: Pulse, blood pressure, respiratory rate, body temperature;
4. Relevant laboratory tests, including blood routine examination: Red blood cell (RBC) count, white blood cell (WBC) count, neutrophil ratio, hemoglobin, platelets, C-reactive protein, etc.;

5. DVC type, site of insertion, duration, documentation of any post-puncture exudation, application of any other products such as gauze, hemostatic pads, etc.;
6. Documentation of skin conditions around the catheter site, scoring with reference to the standards for evaluating local skin irritation as listed in the appendix;
7. Medication use in relation to the trial, including mainly fat emulsions, heparin, blood transfusions and antimicrobial drugs;
8. Adverse events, device defects, complaints.

10.2.3 Follow-up visits (number of visits to be marked if there are multiple visits during each dressing change)

Since the expected use duration of the test/control product is a maximum of 7 days, there will be at least one visit on the seventh day into the trial (if catheterization duration is longer than 7 days), and more visits could be taken on a case-by-case basis. The following procedures will be completed at Follow-up visits:

1. Performing dressing changes in accordance with routine departmental nursing procedures;

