10.2.4 End-of-treatment Visit

Visit following the completion of dressing securement at the insertion site after removal of DVC. A patient who has multiple catheters withdrawn during the trial should be documented sequentially, but the trial is not to be considered complete at least until the CVC is removed. If replacement of the same type of DVC is performed, only the first removal is recorded and the subsequent replacement is not included in the test or observation.

The following procedures will be completed during the end-of-treatment visit:

1. Assessment of dressing securement performance;
2. Assessment of skin conditions around the catheter site, with reference to the standards for evaluating local skin irritation as listed in the appendix;
3. Photographic documentation of any anomalies;
4. Following departmental routine practice, the tip is cut with sterile scissors after removal, while skin sampling around the insertion site is performed. The samples taken are, under aseptic conditions, sent for pathogenic bacteria testing and species analysis.
5. In case of suspected CLABSI/CRBSI occurrence, sampling and quantitative culture for both catheter and peripheral blood will be performed simultaneously, as well as analysis of pathogenic bacteria species, according to diagnostic evaluation criteria.

The following data will be collected during the end-of-treatment visit:

1. Vital signs: Pulse, blood pressure, respiratory rate, body temperature;
2. Relevant laboratory tests, including blood routine examination: Red blood cell (RBC) count, white blood cell (WBC) count, neutrophil ratio, hemoglobin, platelets, C-reactive protein, etc.;
3. Documentation of dressing securement performance;
4. Documentation of skin conditions around the catheter site, including erythema, edema, rash, etc., and scoring with reference to the standards for evaluating local skin irritation as listed in the appendix.

5. Total duration of DVC placement and duration of application of the test/control dressing;
6. Catheter-tip culture and classification of colonies;
7. Culture and classification of colonies from the skin samples around the insertion site;
8. Any changes in medication use relevant to the trial, including mainly fat emulsions, heparin, blood transfusions and antimicrobial drugs;
9. Confirmation of CLABSI/CRBSI diagnosis;
10. Adverse events, device defects, complaints.

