4.1.2 Secondary efficacy indicator

- Number of positive cases per 1,000 catheter-days of bacterial colonization at the tip of the CVC (number of culture-positive catheters/total catheter retention time (days) * 1000%));
- (2) Bacterial colonization rate at the tip of other types of (percutaneous) deep vein catheters and the catheterization site (number of culture positive cases/total catheters x 100% and number of positive cases per 1,000 catheter-days), including hemodialysis, PICCO, float catheters, etc;
- (3) Occurrence of suspected CLABSI/CRBSI, which entails catheter tip bacterial culture and blood bacterial culture
- (4) Securement performance of the dressing: Frequency of dressing changes associated with wearing time and warping or peeling

participant wear time (hours) = sum of all dressing wear times (hours) for the participant/participant dressing changes

Number, where wear time (hours) for each dressing = change date time - use date time.

Replacement due to edge lifting and droping out is defined as whenever there is a dressing replacement due to edge lifting and droping out, it is determined that the participant appears to be replaced.

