6.3 Efficacy Evaluation

6.3.1 Primary Efficacy Evaluation

(1) Evaluation Indicators

Occurrence rate of bacterial colonization of the CVC tip segment and skin at the insertion site after extubation (number of culture-positive cases/total catheters × 100%)

Primary endpoint: Positive rates of catheter tip cultures and sampling cultures of skin surrouding the insertion site in patients with deep vein indwelling catheterization after CVC tubes were removed.

(2) Evaluation method

FAS and PPS were used for both total catheter count and participant level evaluation. If more than one catheter of the same type was available for the same participant and the culture results were inconsistent, a positive culture result was taken for that participant when participant-level analysis was performed.

Describe the number and percentage of cases of bacterial colonization of the CVC tip segment and skin at the insertion site after extubation in both groups, and compare the two groups using a chi-square test or Fisher's exact test.

In addition, because some subject may have two or more than two CVC, which are interrelated, a generalized mixed linear model was developed to evaluate the difference in the occurrence rate of bacterial colonization between the two groups, using the occurrence rate of bacterial colonization of the CVC tip segment after extubation and the occurrence rate of bacterial colonization of the skin at the CVC insertion site after extubation as dependent variables, group as a fixed effect, and insertion site, skin infection of baseline insertion site, and their interaction as random effects, respectively.

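### Pre-randomisation catheter dwell is collected and derived but enters no outcome model, and the start of catheter-days is not stated

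*SAP*

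**What the plan says.** **Catheters before randomisation.** At Visit 1 the protocol (10.2.2) calls for "Performing immediate dressing changes at all DVC insertion sites", so the study dressing can replace one already on the site. The same visit records "DVC type, site of insertion, duration, documentation of any post-puncture exudation".

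**Derived variable.** SAP 6.2.2 defines "Duration of tube insertion (days) = date of randomization", followed by the insertion date and plus one; I read the two dates as a subtraction. The section summarises this duration by insertion site, compares it between groups with a t-test or rank sum test, and lists catheterisation before enrolment.

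**Outcome models.** SAP 6.3.1 fits models to tip colonisation and to skin colonisation with "group as a fixed effect, and insertion site, skin infection of baseline insertion site, and their interaction as random effects". SAP 6.3.2 uses the same terms for the per-1,000-catheter-day rate. Prior dwell appears in none of them.

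**Catheter-days.** SAP 4.1.2 defines the CVC rate as "number of culture-positive catheters/total catheter retention time (days) * 1000" and gives no start date for the retention time. Protocol 10.2.4 records "Total duration of DVC placement and duration of application of the test/control dressing" as two items. SAP 6.2.3.1 only describes these two durations.

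**The concern.** Time in place before the study dressing is exposure to colonisation that the dressing cannot affect. It is fixed before allocation and can differ between patients. By using rates per 1,000 catheter-days, the plan itself treats catheter time as a driver of risk. A baseline variable of this kind is a natural covariate, yet the models adjust for insertion site and baseline skin infection and leave it out.

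Two things are at stake. The group estimate carries avoidable variation from prior dwell, and a chance difference in prior dwell stays in the estimate. Separately, an undefined start for catheter-days leaves the denominator of a secondary endpoint open to choice in an open-label trial.

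**Working it through.** **The plan's own figure.** The documents state no mean, SD or range for prior dwell and no catheter-day total, so there is nothing to reproduce on this point. What follows illustrates scale under labelled assumptions.

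**Inputs from the documents.** Control tip colonisation 18.7%, a 50% reduction (so 9.35%) and 220 per arm (Protocol 19.2; SAP 3.2); 1:1 allocation (Protocol 10.2.1); participation of about 3 to 14 days (Protocol 6.0).

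**Assumptions.** One CVC per subject, a constant colonisation hazard, 7 days' total dwell, and an SD of prior dwell of 1, 2 or 3 days.

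**Step 1: size of a chance imbalance.** The SE of the difference in mean prior dwell is SD × √(2/220) = SD × 0.0953. The 95% range is ±1.96 times that: ±0.19, ±0.37 and ±0.56 days.

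**Step 2: effect of one extra day on the tip proportion.** The hazard is −ln(1 − 0.187)/7 = 0.2070/7 = 0.0296 per day. The slope is 0.0296 × 0.813 = 0.024, or 2.4 percentage points per day. The slope scales inversely with assumed total dwell: 0.2070 × 0.813/3 = 5.6 points per day at 3 days and 0.2070 × 0.813/14 = 1.2 at 14 days.

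**Step 3: shift in the group difference, using the 7-day slope.**

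| SD of prior dwell (assumed) | 95% chance imbalance, days | Shift, percentage points |
|---|---|---|
| 1 | 0.19 | 0.4 |
| 2 | 0.37 | 0.9 |
| 3 | 0.56 | 1.3 |

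The planned difference is 18.7 − 9.35 = 9.35 points. Its SE is √[(0.187 × 0.813 + 0.0935 × 0.9065)/220] = 0.033, or 3.3 points. The shift is therefore about 0.1 to 0.4 of one SE.

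**Step 4: precision.** The share of control-arm outcome variance explained by prior dwell is (0.024 × SD)²/(0.187 × 0.813), which gives 0.4%, 1.5% and 3.4%. The gain is real but small under these assumptions. It would be larger if prior dwell varied more or if the hazard rose with time.

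**Step 5: which denominator matches the numerator.** The tip is cultured once, at removal, and the schedule of events (Protocol 10.3; SAP 3.4) has no baseline tip culture. A positive result therefore reflects the whole dwell. Take 7 days under the study dressing, assumed prior dwell of 1, 3 or 5 days, and 18.7% positive at removal:

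| Prior days (assumed) | Per 1,000 total days: 187/(7 + prior) | Per 1,000 dressing days: 187/7 | Constant hazard per 1,000 days: 207.0/(7 + prior) |
|---|---|---|---|
| 1 | 23.4 | 26.7 | 25.9 |
| 3 | 18.7 | 26.7 | 20.7 |
| 5 | 15.6 | 26.7 | 17.3 |

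The total-time rate sits at 0.187/0.2070 = 0.90 of the hazard in every row. That gap is common to any crude proportion divided by time and does not depend on prior dwell. The dressing-day rate ignores prior dwell, so its excess grows from 3% (26.7/25.9) to 29% (26.7/20.7) and 55% (26.7/17.3). With the same dwell in both arms, the planned rate ratio is 9.35/18.7 = 0.50 on either denominator.

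**The case against.** The best defence is that nothing here is invalid. Allocation is 1:1, so the chi-square or Fisher comparison needs no adjustment. Prior dwell is compared and listed, so an imbalance would be seen, and the models already carry two site-level factors. The documents are also mixed on how many catheters predate randomisation: the synopsis describes catheterisation as given after assignment. Because the SAP formula adds one, a value of 1 day can mean a catheter placed on the day of randomisation.

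All of that stands, and it keeps the point small. But a baseline test shows an imbalance without adjusting for it, and adding the covariate after seeing that test in an open-label trial would be a post hoc choice.

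Three stronger readings are tempting, and the documents support none of them.

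- *Total retention time understates the rates, and dressing days are the right denominator.* This removes prior days from the denominator while keeping every positive in the numerator, so it assumes that nothing was colonised before the study dressing. With no baseline tip culture, that cannot be shown. With balanced dwell, a change of denominator rescales both arms and leaves the ratio alone.
- *The arms are biased.* Randomisation balances prior dwell on average.
- *The trial loses power because the dressing starts late.* That would need prior-dwell values that the documents lack, and neither a covariate nor a new denominator would cure it.

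**Conclusion.** The point holds as a low-priority improvement. Prior dwell is collected and derived but is in none of the tip, skin or rate models. The consequence is some lost precision and uncorrected chance imbalance, with no systematic bias between arms. Under the assumed SDs of 1 to 3 days, a constant hazard and 7 days' total dwell, a 95% chance imbalance shifts the tip difference by roughly 0.4 to 1.3 percentage points, and prior dwell explains at most about 3% of outcome variance. The true size depends on a dwell distribution that the documents do not give.

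Total retention time is a defensible denominator because it covers the same period as the culture result. Insertion is its natural start, but the SAP should say so. No percentage understatement of the rates can be derived from the documents.

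**What to change.** 1. In SAP 6.3.1 and 6.3.2, pre-specify dwell from insertion to randomisation, per catheter, as a fixed covariate in the tip, skin and rate models. State the value to use for a catheter inserted on or after the day of randomisation. The unadjusted chi-square or Fisher comparison can stay as it is.
2. In SAP 4.1.2, state that total catheter retention time runs from insertion to removal, and keep it as the main denominator for catheter-day rates.
3. Add the rate from first study dressing to removal as a sensitivity analysis only, with a note that its numerator can include colonisation acquired before the study dressing.

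The cost is SAP wording and a few lines of code. Protocol 10.2.2 and 10.2.4 already collect the data. The change should be made before the interim analysis at 220 subjects, so that neither the covariate nor the denominator is chosen with results in view.

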6.2.3 Exposure

6.2.3.1 Studied products

Quantitative descriptive statistics (number of cases, mean, standard deviation, median, minimum, maximum) were used to describe the study time (days) for both groups of participants. Quantitative descriptive statistics (number of cases, mean, standard deviation, median, minimum, maximum) were used to describe the total insertion time (h) and total dressing using time (h) for the two groups with different DVC catheters, respectively.

- Duration of study: Study duration is from the date of randomization to the date of completion/withdrawal from the trial when participants were studied on the study summary page.
 - ✓ Study Duration (days) = date of completion/withdrawal from trial date of randomization + 1

6.2.3.2 Pre-treatment and combined medication/treatment

Pre-treatment and combined medications were coded according to the classification of the Dictionary of Contemporary Drug Trade Names and Aliases (organized and edited by the Chinese Pharmaceutical Association, published and distributed by Chemical Industry Press and Modern Biotechnology and Pharmaceutical Technology Publishing Center, 2nd edition, August 2006). Pre-treatment medication is defined as medication prior to the first application of any investigational product. Combined medication was defined as any medication at and after the first application of investigational product. Pre-treatment and combined medications were summarized for each group according to the coded systemic and canonical names, and the number of cases, percentage, and case times were calculated. Details of pre-treatment and combined medications are given in list form.

Pre-treatment and combined treatments were coded according to the latest edition of the Medical Dictionary for Regulatory Activitie (MedDRA) classification. Pre-treatment is defined as treatment prior to the first application of any investigational product. Combination treatment was defined as any treatment at and after the first application of investigational product. The groups were summarized by system organ classification (SOC) and preferred terminology (PT), and the number of cases, percentage, and case times were calculated. Details of pre-treatment and combined treatment are given in list form.

6.3 Efficacy Evaluation

6.3.1 Primary Efficacy Evaluation

(1) Evaluation Indicators

Occurrence rate of bacterial colonization of the CVC tip segment and skin at the insertion site after extubation (number of culture-positive cases/total catheters × 100%)

Primary endpoint: Positive rates of catheter tip cultures and sampling cultures of skin surrouding the insertion site in patients with deep vein indwelling catheterization after CVC tubes were removed.

(2) Evaluation method

FAS and PPS were used for both total catheter count and participant level evaluation. If more than one catheter of the same type was available for the same participant and the culture results were inconsistent, a positive culture result was taken for that participant when participant-level analysis was performed.

Describe the number and percentage of cases of bacterial colonization of the CVC tip segment and skin at the insertion site after extubation in both groups, and compare the two groups using a chi-square test or Fisher's exact test.

In addition, because some subject may have two or more than two CVC, which are interrelated, a generalized mixed linear model was developed to evaluate the difference in the occurrence rate of bacterial colonization between the two groups, using the occurrence rate of bacterial colonization of the CVC tip segment after extubation and the occurrence rate of bacterial colonization of the skin at the CVC insertion site after extubation as dependent variables, group as a fixed effect, and insertion site, skin infection of baseline insertion site, and their interaction as random effects, respectively.

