5.3 Endpoint(s)

5.3.1 Primary Endpoint(s)

The bacterial colonization rate at the CVC tip and the catheterization site on the skin after removal (number of culture-positive cases/total catheters × 100%)

The primary endpoint is the removal of the CVC from the patient with deep vein catheterization to perform catheter-tip culture and sampling and culture of bacteria from the skin around the insertion site.

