6.3.2 Secondary Efficacy Evaluation

- (1) Evaluation Indicators
 - Number of positive cases per 1,000 catheter-days of bacterial colonization at CVC tips;
 - 2) Bacterial colonization rate at the tip of other types of (percutaneous) deep vein

catheters and the catheterization site (number of culture positive cases/total catheters x 100% and number of positive cases per 1,000 catheter-days), including hemodialysis, PICCO, float catheters, etc;

- 3) Occurrence of suspected CLABSI/CRBSI, which entails catheter tip bacterial culture and blood bacterial culture
- 4) Securement performance of the dressing: Frequency of dressing changes associated with wearing time and warping or peeling
- (2) Evaluation method

FAS and PPS were used for evaluation.

Quantitative descriptive statistics (number of cases, mean, standard deviation, median, minimum, maximum) were used to describe the number of positive cases per 1,000 catheter-days occurring in the two groups of CVC tip bacterial colonization, and t-test or rank sum test was used to compare the two groups. In addition, a mixed linear model was developed to evaluate the difference in the number of positive cases per 1,000 catheter days of bacterial colonization between the two groups, using the number of positive cases per 1,000 catheter days of bacterial colonization of the CVC tip segment after extubation as the dependent variable, group as a fixed effect, and insertion site, skin infection of baseline at the insertion site, and their interaction as random effects.

The number and percentage of cases of bacterial colonization at the tip of other types of (percutaneous) deep vein catheters and the catheterization site after extubation were described separately for both groups with the total number of catheters and at the participant level, and the two groups were compared using the chi-square test or Fisher's exact test.

Quantitative descriptive statistics (number of cases, mean, standard deviation, median, minimum, maximum) were used to describe the number of positive cases per 1,000 catheter days occurring at the tip of other types of (percutaneous) deep vein catheters and the catheterization site after extubation in both groups. If more than one catheter of the same type was placed in the same participant, it will be analyzed with the total number of catheters and participant level separately and the two groups will be compared using a t-test or Wilcoxon rank sum test.

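### The SAP's mixed model for correlated CVCs names no participant effect, and neither the primary analysis nor the interim rule says whether catheter or participant level decides

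*SAP*

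**What the plan says.** The primary endpoint has a per-catheter denominator. Protocol 5.3.1 defines it as "The bacterial colonization rate at the CVC tip and the catheterization site on the skin after removal (number of culture-positive cases/total catheters", and the synopsis and SAP 2.1, 4.1.1 and 6.3.1 agree. For its analysis SAP 6.3.1 states that "FAS and PPS were used for both total catheter count and participant level evaluation", using a chi-square or Fisher test. Where a subject's catheters disagree, "a positive culture result was taken for that participant when participant-level analysis was performed".

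The same section then adds a generalized linear mixed model, giving as the reason "because some subject may have two or more than two CVC, which are interrelated". Its terms are "group as a fixed effect, and insertion site, skin infection of baseline insertion site, and their interaction as random effects, respectively".

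SAP 6.3.2 plans a linear mixed model for CVC-tip positives per 1,000 catheter-days, with "group as a fixed effect, and insertion site, skin infection of baseline at the insertion site, and their interaction as random effects". Its provision that multiple catheters of one type "it will be analyzed with the total number of catheters and participant level separately" stands in the paragraph on other catheter types, not in the one on the CVC-tip rate.

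The sample size (Protocol 19.2, SAP 3.2) is 220 patients per group. SAP section 8 times the interim by 220 participants and allows early stopping at p below 0.005 without naming a level of analysis. Protocol 10.2.4 limits repeat catheters: "If replacement of the same type of DVC is performed, only the first removal is recorded and the subsequent replacement is not included".

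**The concern.** A model handles correlation within patients only if something in it identifies the patient. Under the 6.3.1 list, two CVCs in one patient at different insertion sites share no term that marks them as belonging to that patient, while CVCs at the same site in unrelated patients do share one. The model therefore does not do the job given as its reason. The catheter-level chi-square or Fisher test also treats catheters as independent.

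The participant-level any-positive test avoids the problem, but it is one of two unranked analyses of the primary endpoint. The wording points both ways: the endpoint counts catheters, the sample size counts patients. In an open-label trial with an unblinded interim, the choice between two p-values would remain open after results are seen. The two levels also estimate different quantities, because counting a participant as positive on any positive catheter raises the rate.

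At stake is the type I error of the primary comparison and of the early-stopping rule, if the catheter-level result is the one relied on.

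**Working it through.** **Inputs from the documents.** Control rate 18.7%, 50% reduction (9.35% in the test arm), 220 patients per arm, 1:1 allocation (SAP 3.2, 3.3); nominal two-sided levels 0.048 final and 0.005 interim (SAP 6.1, 8).

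**Assumed, because the documents are silent.** Share f of patients with two CVCs: 5 to 30%. Within-patient correlation r: 0.5, range 0.2 to 0.8.

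**The plan's own figure.** With pooled variance, n = [z(α/2)·√(2p̄q̄) + z(β)·√(p1q1 + p2q2)]² / (p1 − p2)². Here p̄ = 0.14025, so √(2p̄q̄) = 0.4911 and √(p1q1 + p2q2) = 0.4866. At α = 0.05, n = (1.960 × 0.4911 + 0.8416 × 0.4866)² / 0.0935², or 216 per arm; at 0.048 it is 219. The stated 220 is therefore a calculation with one observation per patient and no design effect. It reproduces only without the continuity correction that the sample-size text appears to name; with the correction, n is 237 or 239.

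**Error of the catheter-level test by formula.** Design effect DE = [(1 − f) + 2f(1 + r)] / (1 + f), and true α = 2[1 − Φ(1.977/√DE)]. For f = 10% and r = 0.5, DE = (0.90 + 0.30)/1.10 = 1.091 and α = 5.83%.

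**Simulation.** Null trials with 220 patients per arm, 18.7% in both arms and beta-binomial correlation. There were 500,000 trials per setting (Monte Carlo SE about 0.03 points), and 20,000 for Fisher. Values are true error in % at nominal 4.8% and r = 0.5, with the range for r = 0.2 to 0.8 in brackets.

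| Share with two CVCs | Formula | Chi-square | Continuity-corrected | Fisher |
|---|---|---|---|---|
| 5% | 5.34 | 5.3 (5.0–5.7) | 4.0 (3.8–4.3) | 4.3 |
| 10% | 5.83 | 5.9 (5.2–6.4) | 4.6 (4.0–5.0) | 5.1 |
| 20% | 6.71 | 6.8 (5.6–7.9) | 5.3 (4.4–6.4) | 5.8 |
| 30% | 7.47 | 7.4 (5.8–9.1) | 6.0 (4.6–7.5) | 6.7 |

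The participant-level test runs at 4.8–4.9% throughout (3.5–3.6% corrected). Standard errors clustered on participant give 4.9–5.0%.

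**The 6.3.1 model as listed.** Logistic model with random effects crossed over patients, three insertion sites and 2% baseline infection assumed, about 7,000 trials per share (SE about 0.3). For shares of 5 / 10 / 20 / 30% the error is 5.5 / 5.7 / 6.2 / 7.4%, against 5.7 / 5.8 / 6.3 / 7.6% for chi-square on the same data. With no two-CVC patients it is 4.9%. On this reading the model removes almost none of the excess.

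**Interim, nominal 0.5%, 110 patients per arm, r = 0.5.** Uncorrected chi-square 0.58 / 0.69 / 0.88 / 1.12%; corrected 0.34 / 0.42 / 0.55 / 0.74%; participant level 0.46–0.48%.

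**The 6.3.2 CVC-tip rate, analysed per catheter.** Value 1000 × positive/days, with days assumed uniform on 3–14.

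| Analysis | Same dwell time for both CVCs | Independent dwell times |
|---|---|---|
| t-test | 5.4 / 5.9 / 6.9 / 7.6% | 5.2 / 5.6 / 6.2 / 6.8% |
| Mixed model as listed (SE about 0.25) | 5.9 / 5.8 / 6.7 / 8.0% | 5.6 / 5.8 / 6.1 / 6.8% |

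Participant level gives 4.8–4.9%.

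**The two levels differ as estimands.** With f = 20% and r = 0.3, the chance that both CVCs are positive is 0.187² + 0.3 × 0.187 × 0.813 = 0.0806. The any-positive control rate is 0.8 × 0.187 + 0.2 × (0.374 − 0.0806) = 20.8%, against 18.7% per catheter.

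**The case against.** The strongest reply has four parts.

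- **The level is implied.** The endpoint is defined per catheter throughout, and section 8 tests the primary endpoint, so catheter level could be inherited. The patient counts may be only recruitment and timing targets. That is a fair reading, but 6.3.1 still runs both levels without ranking them. If catheter level does decide, the unclustered test becomes the main result.
- **The model text is narrative, not code.** Since correlation within subjects is the stated reason, the authors may intend the random effects to be nested within participant. For two CVCs with the same infection status, a nested infection effect would act much like a participant intercept. The model simulations cover only the crossed reading. The SAP does not state the nesting, and it must.
- **6.3.2 is weaker ground.** It is a secondary endpoint, no correlation rationale is given there, and the unit is unstated, so the inflation arises only if values are per catheter. The dwell times come from the 3–14 day participation period, although SAP 6.2.2 shows that catheters may be inserted before randomization. All of this stands and limits the figures; the missing unit remains.
- **The harm is probably small.** The model is supplementary, a valid participant-level test exists, and Protocol 10.2.4 leaves mainly concurrent CVCs. With the continuity correction the final error is at most 5.0% up to a 10% share. This stands too, but SAP 6.3.1 does not say that its chi-square test is corrected.

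**Conclusion.** The concern holds. As written, no catheter-level analysis in 6.3.1 accounts for correlation between a patient's CVCs, although the model was added for that purpose. The 6.3.2 CVC-tip model has the same structure and no stated participant-level alternative. Neither 6.3.1 nor section 8 names the deciding level. These are facts of the text and depend on no assumption.

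The size does depend on assumptions: the share of patients with two CVCs, the correlation and, for the models, site count, infection rate and dwell time. For shares of 5 to 10% at correlation 0.5, uncorrected error is 5.3 to 5.9% against 4.8%, and corrected error is 4.0 to 4.6%. The 20% and 30% rows are upper scenarios that no figure in the documents supports. The expected harm is therefore modest, but the defect sits in the primary analysis and is easily removed, so it should be fixed.

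**What to change.** - In SAP 6.3.1 and 6.3.2, add a participant random intercept, or use GEE or cluster-robust standard errors by participant, for every catheter-level comparison. The insertion-site and baseline-infection terms may stay. If nesting within participant was intended, state it.
- Before any unblinded comparison, including the interim, name one decisive level for the primary endpoint: either the participant-level test already planned or the participant-clustered catheter-level test. Use the same level for the p-value in section 8.
- In 6.3.2, state the unit of analysis for the CVC-tip rate.
- Report how many patients per arm have two or more counted CVCs.

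The cost is a few sentences and a changed model statement in 6.3.1 and 6.3.2, plus one sentence in section 8; no new data are needed. Choosing the participant level matches the patient-based sample size, but the per-catheter endpoint wording in Protocol 5.1, 5.3.1 and the synopsis, and in SAP 2.1, 4.1.1 and 6.3.1, would have to be aligned. Choosing the clustered catheter-level test avoids that.
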